### **13.6.2. Preparation, Handling, Storage, Accountability, and Dispensing**

Refer to master protocol [Section 6.2](#).

For axitinib, the participant/caregiver should be instructed to maintain the tablets in the bottles provided throughout the course of dosing and return the bottles to the site at the next study visit.

Please refer to the IP manual for further instructions on the preparation and handling of axitinib and SEA-TGT.

### **13.6.3. Measures to Minimize Bias: Randomization and Blinding**

This is an open-label sub-study that will not be randomized.

#### **13.6.3.1. Allocation to Study Intervention**

Refer to master protocol [Section 6.3.1](#).

#### **13.6.4. Study Intervention Compliance**

Refer to master protocol [Section 6.4](#).

SEA-TGT must be administered by the appropriately designated study staff at the investigational site and compliance will be documented. Deviation(s) from the prescribed dosage regimen should be recorded in the eCRF.

### **13.6.5. Concomitant Therapy for Sub-Study B**

In addition to concomitant therapy instructions and restrictions in the master protocol [Section 6.5](#), the following concomitant therapy instructions and restrictions apply to [Sub-Study B](#).

#### **13.6.5.1. Permitted Concomitant Therapy Requiring Caution and/or Action**

##### **13.6.5.1.1. CYP and UGT Substrates and Inhibitors**

Axitinib is metabolized primarily in the liver by CYP3A4/5 and to a lesser extent by CYP1A2, CYP2C19, and UGT1A1. Concomitant use of strong CYP3A4/5 inhibitors should

be avoided in Phase 1b of Sub-Study B as adjusting the axitinib dose during the DLT period could confound dose selection. If concomitant use of a strong CYP3A4/5 inhibitor is unavoidable in Phase 2, consultation with the sponsor is needed prior to concurrent use of the strong CYP3A4/5 inhibitor as the dose of axitinib will need to be adjusted by approximately one-half. Selection of an alternate concomitant medication with no or minimal enzyme inhibition and/or induction potential is recommended in Sub-Study B when co-administered with axitinib.

Participants must avoid consumption of grapefruit, pomegranates, Carambola (starfruit), Seville oranges or products containing the juice of any during the entire study and preferably starting 7 days before the first dose of study interventions, due to potential CYP3A4/5 interaction with axitinib.

For examples of drugs of CYP3A inhibitors to be used with caution or avoided, please see [Section 10.13](#).

#### **13.6.5.2. CYP3A Inducers**

Coadministration of axitinib with strong systemic CYP3A4/5 inducers (eg, rifampin, dexamethasone, phenytoin, carbamazepine, rifabutin, rifapentin, phenobarbital, and St. John's wort) are prohibited throughout the study (Phase 1 and Phase 2). Selection of concomitant medication with no or minimal CYP3A4/5 induction potential is recommended. Moderate CYP3A4/5 inducers (eg, bosentan, efavirenz, etravirine, modafinil, and nafcillin) may also reduce the plasma exposure of axitinib and should be avoided if possible. For examples of moderate and/or strong CYP3A4 inducers, see [Section 10.13](#).

#### **13.6.5.3. Supportive Care**

Participants who need to be on anticoagulant therapy during axitinib treatment should be treated with low molecular weight heparin. If low molecular weight heparin cannot be administered, coumadin or other coumarin derivatives or other anti-coagulants (including direct Xa inhibitors and direct thrombin inhibitors) may be allowed; however, appropriate monitoring of prothrombin time/international normalized ratio (PT/INR) should be performed.

#### **13.6.5.4. Surgery**

See [Section 6.5.7](#) for master protocol surgery restrictions. If a major surgery or an interventional procedure (eg, endoscopy) is required, treatment with axitinib must be interrupted at least 2 days before the procedure and the patient BP should be monitored closely for hypotension. Patients may resume axitinib 2 weeks after major surgery assuming the wound has completely healed and there are no wound healing complications (eg, delayed healing, wound infection or fistula).

#### **13.6.6. Dose Interruptions and Modifications for Sub-Study B**

During the study, any adverse event considered to be related to treatment needs to be further assessed for the potential causality to which of the 3 investigational products. Dose interruption and modification are performed accordingly as explained below.

### 13.6.6.1. SEA-TGT Dose Modifications

In the event of drug-related toxicity during SEA-TGT therapy, dosing may be delayed and/or reduced as described in [Section 13.10.4](#). SEA-TGT dose delays >21 days should be discussed with the medical monitor. If clinical benefit is demonstrated, subsequent treatment with SEA-TGT may be at a reduced dose level or a prolonged dose interval. The type and severity of the AE observed will be taken into consideration to inform the decision. Participants who experience AEs that meet the criteria for permanent discontinuation of SEA-TGT may not resume SEA-TGT, including at a lower or modified dose.

#### 13.6.6.1.1. Infusion-Related Reactions

IRRs usually occur within 24 hours of infusion and may manifest as a combination of signs or symptoms including fever, rigors, flushing, itching, various types of rash, urticaria, dyspnea, nausea, vomiting, back or abdominal pain, and/or hypotension. IRRs may occur during the infusion of SEA-TGT. The infusion should be administered at a site properly equipped and staffed to manage anaphylaxis. Dose modifications and management of IRRs are in [Section 13.10.4](#).

All supportive measures consistent with optimal participant care should be given throughout the study according to institutional standards. Supportive measures may include, but are not limited to, any or all of the following:

- Slowing, interruption, or other adjustments in the administration of SEA-TGT
- Potential premedication or postmedication for infusions, for example:
  - Antihistamines, such as diphenhydramine 50 mg IV or equivalent
  - Famotidine 40 mg IV or equivalent
  - Antipyretics, such as acetaminophen 500–1,000 mg PO
  - Antiemetics, such as ondansetron
  - IV fluid support, such as normal saline
  - Anti-rigor medication, such as meperidine
  - Vasopressors
  - Corticosteroids, such as hydrocortisone 100 mg IV or equivalent, or methylprednisolone 40 mg IV or equivalent (See [Master Section 6.5.6](#) regarding steroid use in this study)

#### 13.6.6.1.2. Allergic/ Hypersensitivity Reactions

Allergic/hypersensitivity reactions to SEA-TGT are differentiated from IRRs to SEA-TGT by being defined as occurring >24 hours after infusion of SEA-TGT. Allergic/hypersensitivity reactions may manifest in the same manner as IRRs. All participants should be closely observed while receiving SEA-TGT, and after administration in accordance with [Section 13.6.1.2](#). Guidance on SEA-TGT dose modifications is in [Section 13.10.4](#).

See [Section 6.6.1](#) for further information on hypersensitivity reactions.

### 13.6.6.1.3. Cytokine Release Syndrome

Cytokine release syndrome (CRS) is an acute inflammatory response characterized by fever and may be accompanied by multiple organ dysfunction. ASTCT grading will be used for CRS events, and grading is dependent on the degree of supportive care needed. Grades 1 and 2 have fever with or without constitutional symptoms that require less intensive care. Grade 3 and above require more intensive care, such as vasopressors and high percentage oxygen therapy. Dose modifications and management of CRS are in [Section 13.10.4](#). Monitoring and additional support should be performed per institutional practice.

### 13.6.6.2. Axitinib Dose Modifications

In the event of drug-related toxicity during axitinib therapy, dosing may be delayed and/or reduced as described in [Section 13.10.5](#). Recommended axitinib dose reductions are provided in Table 28.

The dose of axitinib will also be adjusted for participants with concomitant CYP3A4/5 inhibitor as specified in [Section 13.6.5.1.1](#).

**Table 28. Dose Reductions for Axitinib for Toxicity Management**

Axitinib Starting Dose	Axitinib First Dose Reduction	Axitinib Second Dose Reduction
3 mg BID	2 mg BID	N/A
5 mg BID	3 mg BID	2 mg BID

NOTE: Dose reduction should be based on the highest AE grade.

#### 13.6.6.2.1. Management of Axitinib-Related Hypertension

Patients should contact the site for guidance if their systolic BP rises above 150 mm Hg, diastolic BP rises above 100 mm Hg, or if they develop symptoms perceived to be related to elevated BP (eg, headache, visual disturbance). To treat an increase in BP, standard antihypertensives can be used (eg, thiazide or thiazide-like diuretics, angiotensin II receptor blockers, angiotensin converting-enzyme inhibitors, or dihydropyridine [DHP] calcium channel blockers). Bradycardic agents (eg, beta adrenergic blockers with or without alpha-blocking properties, and non-DHP calcium channel blockers, clonidine, digoxin) should be avoided to the extent possible (See concomitant restrictions in [Section 13.6.5](#)).

#### 13.6.6.2.2. Bleeding Risks

The sponsor should be contacted to consider permanent discontinuation of axitinib if a patient develops symptomatic brain metastasis, tumor encasing vasculature, hemoptysis, or other risks for pulmonary hemorrhage while on study treatment. If brain metastases are successfully treated or if participant no longer needs anticoagulation or bleeding disorders resolve, then the treatment could be re-started at the discretion of the investigator and upon discussion with the sponsor.

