Thrombocytopenia Grade ≥3 (platelets <50,000/μL)	Hold sasanlimab and monitor weekly until resolution to Grade ≤1 or baseline. Resume sasanlimab at the next scheduled dose after recovery to Grade ≤1 or baseline. Permanently discontinue sasanlimab if thrombocytopenia does not resolve to Grade ≤1 or baseline within 12 weeks or if the same Grade 3 toxicity recurs.
Non-hematologic toxicities	
Grade 1	Continue as per schedule.
Grade 2	First occurrence: continue per schedule. Follow modifications for Grade 3 event if Grade 2 AE is considered intolerable and recurrent based on medical judgment.
Grade 3	Hold sasanlimab. Resume sasanlimab at the next scheduled dose after recovery to Grade ≤1 or baseline. Permanently discontinue if toxicity does not resolve to Grade ≤1 or baseline within 12 weeks or if the same Grade 3 toxicity recurs. Exceptions are: laboratory values that do not have any clinical correlate. For suspected immune-related toxicity follow guidance in Section 10.10 .
Grade 4	Permanently discontinue sasanlimab. Exceptions are: laboratory values that do not have any clinical correlate. For suspected immune-related toxicity follow guidance in Section 10.10 .

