Grade 3	
Interrupt dosing of encorafenib and binimetinib until resolved to Grade <math>\leq</math>1. Resume treatment at 1 reduced dose level of encorafenib. Resume treatment with binimetinib at the current dose if, in the judgment of the investigator, the toxicity is considered to be unrelated to binimetinib, or at 1 reduced dose level.
 
Note: Interrupt dosing of encorafenib and binimetinib for <math>\geq</math>Grade 3 vomiting or Grade 3 nausea only if the vomiting or nausea cannot be controlled with optimal antiemetics (as per local practice).

Severity of Adverse Event	Dose Modifications
Grade 4	Permanently discontinue encorafenib and binimetinib.
Other Adverse Reactions (including renal, hemorrhage)	
Recurrent Grade 2 or First occurrence of any Grade 3	Withhold for up to 4 weeks. 
 
• If improves to Grade 0-1 or to pretreatment/baseline levels, resume at reduced dose.
 
• If no improvement, permanently discontinue encorafenib and binimetinib.
 

First occurrence of any Grade 4	Permanently discontinue or withhold for up to 4 weeks. 
 
• If improves to Grade 0-1 or to pretreatment/baseline levels, then resume at a reduced dose.
 
• If no improvement, permanently discontinue encorafenib and binimetinib.
 

Recurrent Grade 3	Consider permanently discontinuing encorafenib and binimetinib.
Recurrent Grade 4	Permanently discontinue encorafenib and binimetinib.

\*For adverse events that may be related to both encorafenib and binimetinib, guidance is provided for the other agent also.

\*\* Refer to [Section 12.6.6](#) for management of potential overlapping toxicities. Any adverse event suspected to be immune-related should be managed accordingly as in [Sections 6.6](#) and [10.10](#). Consult appropriate specialist as indicated.

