Recurrent Grade 2 or First occurrence of any Grade 3	
Withhold for up to 4 weeks.
 
 
• If improves to Grade 0-1 or to pretreatment/baseline levels, resume at reduced dose.
 
• If no improvement, permanently discontinue binimetinib and encorafenib.
 

First occurrence of any Grade 4	
Permanently discontinue or withhold for up to 4 weeks.
 
 
• If improves to Grade 0-1 or to pretreatment/baseline levels, then resume at a reduced dose.
 
• If no improvement, permanently discontinue binimetinib and encorafenib.
 

Recurrent Grade 3	Consider permanently discontinuing binimetinib and encorafenib.
Recurrent Grade 4	Permanently discontinue binimetinib and encorafenib.

\*For adverse events that may be related to both binimetinib and encorafenib, guidance is provided for the other agent also.

\*\* Refer to Section 12.6.6 for management of potential overlapping toxicities. Any adverse event suspected to be immune-related should be managed accordingly as in Sections 6.6 and 10.10. Consult appropriate specialist as indicated.

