**13.6.1.1. Administration of Axitinib**

Axitinib will be swallowed whole with a glass of water and with or without food. Axitinib should be taken 12 ± 2 hours apart in the morning and in the evening at approximately the

same times every day. If a participant vomits at any time after dosing, the dose should not be re-administered, and the participant should take the next scheduled dose. Any missed dose may be taken up to 3 hours before the next scheduled dose, otherwise it should be skipped. Doses that are omitted for AEs should not be made up during the day, or at the end of the dosing period. Additional information regarding axitinib administration is provided in the IP Manual.

Axitinib will begin on Cycle 1 Day 1 and will be self-administered at home twice per day continuously, except on study visit days, when it should be administered at the study site.

Axitinib intra-patient dose increase is permitted in Phase 1b and Phase 2 after completing 16 weeks of axitinib treatment for participants who tolerate the current axitinib dose with no Grade  $\geq 2$  drug-related adverse events for 2 consecutive weeks, and have blood pressure  $\leq 150/90$  mm Hg, and are not receiving antihypertensive medication. These participants will have the option to have their axitinib dose increased by one dose level in subsequent cycles, up to a maximum dose of 10 mg BID; the available doses are 3 mg BID, 5 mg BID, 7 mg BID, and 10 mg BID. Particular attention should be provided to a patient's overall safety profile prior to implementing intra-patient dose increase for axitinib.

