### 13.10.4. Recommended Dose Modification and Management of SEA-TGT-related Adverse Events

Toxicity	NCI CTCAE Severity Grade	SEA-TGT Dose Modification & AE Management
Hepatotoxicity	ALT and/or AST elevation >3 x ULN and total bilirubin >2 x ULN	Discontinue SEA-TGT.
	ALT and/or AST elevation >3 x ULN with the appearance of clinical symptoms of hepatic injury	Discontinue SEA-TGT.
Other	Grade 3	Withhold SEA-TGT dose until toxicity is Grade $\leq$ 2 or returns to baseline, and then resume treatment at the same dose level after discussion with the medical monitor/Sponsor.
	Grade 4	Withhold SEA-TGT dose until toxicity is Grade $\leq$ 2 or returns to baseline. Either resume treatment at a lower dose level after discussion with medical monitor or discontinue study treatment at the discretion of the investigator.
IRR, allergic reaction, or anaphylaxis  or  CRS*	Grade 1	Monitor vital signs more frequently until symptoms have resolved and subject is medically stable. Administer symptomatic treatment as medically indicated.  Consider premedication with subsequent SEA-TGT treatment.
	Grade 2	Hold SEA-TGT treatment. Monitor vital signs more frequently until symptoms have resolved and subject is medically stable. Administer symptomatic treatment as medically indicated. If subject responds promptly and is medically stable in the opinion of the investigator, SEA-TGT treatment may be continued at a slower rate.  Consider premedication with subsequent SEA-TGT treatment. Consider slower infusion rate. If recurrent after the above measures, consider dose reduction to 1 dose level below current dose.
	Grade 3	Stop SEA-TGT treatment. Institute additional medical management as indicated.

Toxicity	NCI CTCAE Severity Grade	SEA-TGT Dose Modification & AE Management
		Subjects with an IRR that resolves to baseline or Grade $\leq 1$ within approximately 2 hours after intervention may continue SEA-TGT at a reduced dose for subsequent infusions, if approved by the sponsor/medical monitor.  OR  Permanently discontinue SEA-TGT.
	Grade 4	Permanently discontinue SEA-TGT.

\* ASTCT grading will be used for CRS (CTCAE will be used for all other adverse events)  
 Note: For detailed irAE management guidelines, refer to [Section 10.10](#).

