### 13.10.5. Recommended Dose Modifications for Axitinib-related Adverse Events

Toxicity	NCI CTCAE Severity Grade	Axitinib Dose Modification
Hematologic Laboratory Abnormalities	Grade 4	Withhold until recovery to Grade $\leq 2$ . Then, reduce by 1 dose level and resume treatment. Grade 4 lymphopenia not associated with clinical events, eg, opportunistic infection: study treatment may continue without interruption.
AST, ALT with total bilirubin $< 2 \times$ ULN and PT/INR $< 1.5 \times$ ULN	Grade 2	Withhold until resolution to $< 2 \times$ ULN or baseline. Restart at same dose level or one lower dose level.
	Grade 3 and 4	Withhold until resolution to $< 2 \times$ ULN or baseline. Restart at one lower dose level.
AST/ALT Elevation with clinically significant hepatic dysfunction (ie, total bilirubin $\geq 2 \times$ ULN excluding biliary obstruction or PT/INR $\geq 1.5 \times$ ULN)		Permanently discontinue axitinib.
Non-hematologic Toxicities, Laboratory Abnormalities and/or Other Drug Related Toxicities	Grade 3	Reduce by 1 dose level.  Grade 3 toxicities controlled with symptomatic medications, or Grade 3 asymptomatic biochemistry (other than LFTs) laboratory abnormalities may continue at the same dose level per Investigator judgment.
	Grade 4	Other non-hematologic/laboratory and non-laboratory abnormalities: hold treatment until recovery to Grade $\leq 2$ then reduce by 1 dose level and resume treatment.  Grade 4 asymptomatic biochemistry laboratory (other than LFTs) abnormality: study treatment may continue without interruption per Investigator's judgment.
Proteinuria	dipstick shows $\geq 2+$	Perform 24-hour urine collection. Dosing may continue while waiting for test results.
	$\geq 2$ g proteinuria/24 hours	Withhold until proteinuria is $< 2$ g/24 hours. Repeat 24-hour urine collection for proteinuria and creatinine clearance (interval at Investigator discretion) until proteinuria is $< 2$ g/24 hours. Then resume at the same dose level or reduce by 1 dose level as per Investigator judgment.

Toxicity	NCI CTCAE Severity Grade	Axitinib Dose Modification

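### Sub-Study B's axitinib rules order no interim hold for hemoptysis, other pulmonary-hemorrhage risks or a related Grade 3 bleed

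*Protocol*

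**What the plan says.** Section 13.6.6.2.2 (Bleeding Risks) opens: "The sponsor should be contacted to consider permanent discontinuation of axitinib if a patient develops symptomatic brain metastasis, tumor encasing vasculature, hemoptysis", and adds other risks for pulmonary hemorrhage. It then allows a restart, at the investigator's discretion and after talking to the sponsor, once brain metastases have been treated, anticoagulation is no longer needed or a bleeding disorder has resolved.

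Section 13.6.6.2 says that axitinib may be delayed or reduced for drug-related toxicity, and refers to Section 13.10.5 for how. The Grade 3 row there for non-hematologic and other drug-related toxicities says to go down one dose level. It adds: "Grade 3 toxicities controlled with symptomatic medications, or Grade 3 asymptomatic biochemistry (other than LFTs) laboratory abnormalities may continue at the same dose level", at the investigator's judgment. At Grade 4 the same category is held until Grade 2 or less and then resumed one level lower.

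For the two partner drugs, Table 2 in Section 6.6 says of a related Grade 3 non-hematologic event: "Hold sasanlimab. Resume sasanlimab at the next scheduled dose after recovery to Grade" 1 or less, or baseline. Section 13.10.4 says for other Grade 3 toxicities: "Withhold SEA-TGT dose until toxicity is Grade" 2 or less, or baseline.

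Section 6.6 assigns modifications to each drug by causality. It makes Table 2 and the sub-study appendix the basis for them unless investigator and sponsor expressly agree otherwise.

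**The concern.** The restart sentence in Section 13.6.6.2.2 presupposes a stop that nothing in the section orders. A site reading it for a participant with new hemoptysis learns whom to call, but not whether to give the evening dose. It then turns to Section 13.10.5 and, for a Grade 3 bleed, finds a reduction.

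The protocol treats these risks as serious elsewhere. Section 13.5.2 excludes a history of Grade 2 or higher hemoptysis, central lung lesions involving major vessels, and significant bleeding in the 30 days before the first dose. Under Section 4.3.3, a related Grade 3 bleed in Cycle 1 of Phase 1b would count as a dose-limiting toxicity, because none of the listed exceptions covers it.

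The restart sentence has a second fault. Its anticoagulation condition matches no trigger in the sentence before it, and Section 13.6.5.3 allows anticoagulation during axitinib treatment, with low molecular weight heparin preferred.

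What is at stake is participant safety. The primary analysis is not affected.

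**Working it through.** No sample size, rate or error probability is involved, so the check sets the rules side by side.

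**1. Is a stop ordered in Section 13.6.6.2.2?** The first sentence orders sponsor contact with permanent discontinuation to be considered. The second sets restart conditions. Neither orders an interruption.

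**2. Does Section 13.10.5 supply one?** Counting one row per toxicity and severity level:

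| Action | Rows | Count |
|---|---|---|
| Hold | Grade 4 hematologic; Grade 2 AST/ALT; Grade 3-4 AST/ALT; Grade 4 non-hematologic; proteinuria of 2 g/24 h or more; BP above 160 systolic or 105 diastolic; Grade 2 immune-related; Grade 3-4 immune-related | 8 |
| Permanent discontinuation | AST/ALT elevation with hepatic dysfunction | 1 |
| Neither | Grade 3 non-hematologic; dipstick proteinuria; BP above 150 or 100; recurrent hypertension | 4 |

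8 + 1 + 4 = 13 rows. None names bleeding, and a related Grade 3 bleed falls in one of the four rows with neither action. The table does use holds freely, including for proteinuria and blood pressure.

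**3. The same related Grade 3 bleed, by drug, within Sub-Study B:**

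| Drug | Written action if related to that drug |
|---|---|
| Axitinib | Reduce one level, or same dose if controlled (investigator's judgment) |
| Sasanlimab | Hold |
| SEA-TGT | Withhold |

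If the bleed is attributed to all three drugs, two are held and axitinib continues. If it is attributed to axitinib alone, the tables hold nothing.

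**4. What would a hold cost and achieve?** Axitinib is taken twice daily, so a 24-hour hold costs 2 doses. Section 13.10.5 gives a plasma half-life of 2-4 hours. Assuming simple first-order elimination, the fraction left after 24 hours is 0.5^(24/4) = 0.5^6 = 1.6% at the long end and 0.5^(24/2) = 0.5^12 = 0.02% at the short end. A precautionary hold takes effect within a day.

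**5. Who is exposed?** Section 13.9.1.3 plans about 80 participants (20 in Phase 1b and 60 in Phase 2), and axitinib is part of both the doublet and the triplet.

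**The case against.** The best case for the plan is that Section 13.6.6.2.2 is the specific rule. It applies to hemoptysis of any grade, it starts from permanent discontinuation, which goes further than a hold, and its restart wording shows that a stop was intended. Section 8 requires safety issues to be discussed with the sponsor immediately. Section 13.6.6.2 permits delay, Section 13.10.5 is headed as recommended, and an investigator may hold on judgment. All of this stands and limits the point to the written default. It does not supply the missing instruction. The general text in Section 6.6 on stopping at once does not supply it either: it sits under the sasanlimab heading and applies to events that meet withhold criteria, and Section 13.10.5 has no such criterion for a Grade 3 bleed.

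The comparison with the partner drugs also has limits. Sasanlimab has no dose reductions, and both antibodies are given once per 21-day cycle, so a hold may cost no dose. Axitinib is a twice-daily tablet with reduction levels, and a different default for Grade 3 toxicity in general is reasonable. That is a weaker argument for bleeding on a VEGFR inhibitor.

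A reader might infer three stronger claims that the documents do not support:

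- *That dosing continues through a new symptomatic brain metastasis.* This would normally be progression. Section 7.1 lists objective progression among the reasons for permanent discontinuation. Section 7.1.1 allows treatment beyond it only without clinical signs or symptoms of progression, and without progressive tumor at a critical site that needs urgent intervention. That case is mostly covered.
- *That axitinib is the exception among all five study drugs.* Encorafenib and binimetinib do have a Grade 3 rule of "Withhold for up to 4 weeks", but they belong to Sub-Study A and are never given with axitinib.
- *That a participant bleeding at 10 mg BID would continue at 7 mg BID, above the starting dose.* This reads the escalation list in Section 13.6.1.1 ("the available doses are 3 mg BID, 5 mg BID, 7 mg BID, and 10 mg BID") as a reduction ladder. Table 28, the only reduction table for axitinib, is keyed to the starting dose and sends a 5 mg starter to 3 mg. At most it is silent on escalated participants.

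**Conclusion.** The point holds as a gap in the written rules, mainly for hemoptysis and other Grade 3 bleeding. Section 13.6.6.2.2 orders no interim hold. Section 13.10.5 answers a related Grade 3 bleed with a reduction or no change, while both partner drugs in the same sub-study are held for a Grade 3 event related to them. The anticoagulation restart condition has no trigger.

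This assumes that a bleed is classed with non-hematologic or other drug-related toxicities, the only row that fits, and that it is judged related to the drug concerned. The comparison covers Grade 3 events only and does not extend to low-grade hemoptysis. About 80 participants are exposed. The documents give no bleeding rate, so the number affected cannot be estimated.

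A reader might also infer that axitinib must be stopped for good at Grade 4, or that a restart should be capped at 5 mg BID. Those are clinical preferences. The axitinib Investigator's Brochure, the reference safety document, is not at hand, and nothing in the protocol requires either.

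**What to change.** Three edits in Sub-Study B:

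1. **Section 13.6.6.2.2, first sentence.** *Hold axitinib and contact the sponsor to decide on permanent discontinuation* for Grade 2 or higher hemoptysis, tumor encasing vasculature or another pulmonary-hemorrhage risk. For Grade 1 hemoptysis, contact the sponsor. The Grade 2 threshold matches the hemoptysis exclusion in Section 13.5.2. Leave symptomatic brain metastasis as a trigger for sponsor contact, read with Sections 7.1 and 7.1.1.
2. **Section 13.10.5.** Add a hemorrhage row: at Grade 3, withhold axitinib until recovery, then restart one level lower after discussion with the sponsor. The table's Grade 4 hematologic row already uses this pattern after its hold: "Then, reduce by 1 dose level and resume treatment". The sponsor should state which grade counts as recovery.
3. **Section 13.6.6.2.2, restart sentence.** Delete the anticoagulation condition, or add the trigger that it answers and reconcile it with Section 13.6.5.3.

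The cost is one rewritten paragraph, one table row and some missed axitinib doses (2 for each day held). Analysis, sample size and data collection do not change.
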